APPENDIX B. EASTERN COOPERATIVE ONCOLOGY GROUP PERFORMANCE STATUS

| Grade | Performance Status |
|-------|--|
| 0 | Fully active, able to carry on all predisease performance without restriction. |
| 1 | Restricted in physically strenuous activity but ambulatory and able to carry out work of a light or sedentary nature, eg, light house work, office work. |
| 2 | Ambulatory and capable of all self-care but unable to carry out any work activities. Up and about more than 50% of waking hours. |
| 3 | Capable of only limited self-care, confined to bed or chair more than 50% of waking hours. |
| 4 | Completely disabled. Cannot carry on any self-care. Totally confined to bed or chair. |
| 5 | Dead. |

Source: [Oken et al 1982](#).

APPENDIX C. CYTOCHROME P450 AND P-GLYCOPROTEIN INHIBITORS AND CYTOCHROME P450 INDUCERS

The Food and Drug Administration (FDA) Drug Development and Drug Interactions: Table of Substrates, Inhibitors and Inducers.

<https://www.fda.gov/Drugs/DevelopmentApprovalProcess/DevelopmentResources/DrugInteractionsLabeling/ucm093664.htm#table3-3>. Accessed July 9, 2019.

APPENDIX D. INSTRUCTION TO PARTICIPANTS FOR HANDLING ITACITINIB IR

The participant must be instructed in the handling of itacitinib as follows:

- Store the itacitinib IR at room temperature, in a safe place, and out of the reach of children.
- Only remove the number of tablets needed at the time of administration.
- Not to remove tablets in advance of the next scheduled administration.
- Make every effort to take doses on schedule.
- Report any missed tablets and/or doses.
- To take itacitinib IR with a full glass of water.
- If the participant vomits after taking itacitinib IR, the participant should not take another dose.
- To keep itacitinib IR in a safe place and out of reach of children.
- To bring all used and unused itacitinib IR bottles/kits to the site at each visit.
- To refrain from taking study medication on the day of clinic visits until after blood samples are collected.
- To fast on the day of PK assessments.
- If an itacitinib IR dose is missed by more than 8 hours, that dose should be skipped and the next scheduled dose should be administered at the usual time.

APPENDIX E. MANAGEMENT OF POTENTIAL HY'S LAW CASES

INTRODUCTION

During the course of the study, the investigator will remain vigilant for increases in liver biochemistry. The investigator is responsible for determining whether a participant meets PHL criteria at any point during the study.

The investigator participates, in conjunction with Incyte clinical project and pharmacovigilance representatives, in the review and assessment of cases fulfilling PHL criteria to ascertain whether there is an alternative explanation for the elevations in liver biochemistry other than drug-induced liver injury caused by the study drug.

The investigator fulfills requirements for the recording of data pertaining to PHL or Hy's law cases and AE/SAE reporting according to the outcome of the review and assessment in line with standard safety reporting processes.

DEFINITIONS

For the purpose of this process, definitions are as follows:

Potential Hy's Law

An increase in AST or ALT $> 3 \times$ ULN and total bilirubin $> 2 \times$ ULN at any point during the study. The elevations do not have to be at the same time or within a specified timeframe.

Hy's Law

An increase in AST or ALT $\geq 3 \times$ ULN and total bilirubin $> 2 \times$ ULN, where no other reason can be found to explain the combination of increases (eg, elevated serum ALP indicating cholestasis, viral hepatitis, another drug).

ACTIONS REQUIRED IN CASES OF AST OR ALT $> 3 \times$ ULN OR TOTAL BILIRUBIN $\geq 2 \times$ ULN

Identification and Determination of Potential Hy's Law

To identify cases of AST or ALT $> 3 \times$ ULN or total bilirubin $> 2 \times$ ULN and consequently determine whether the participant meets PHL criteria, please follow the instructions below:

- Review the laboratory report and if a participant has AST or ALT $> 3 \times$ ULN OR total bilirubin $> 2 \times$ ULN at any visit:
 - Determine without delay whether the participant meets PHL criteria by reviewing laboratory reports from all previous visits.
 - Enter the laboratory data into the laboratory eCRF as soon as possible.

Potential Hy's Law Criteria Not Met

If the participant has NOT had AST or ALT $\geq 3 \times$ ULN AND total bilirubin $> 2 \times$ ULN at any point in the study (the elevations do not have to be at the same time or within a specified timeframe), irrespective of ALP, please follow the instruction below:

- Perform follow-up on subsequent laboratory results according to the guidance provided in Section [6.6.3](#) of the Protocol.

Potential Hy's Law Criteria Met

If the participant has had AST or ALT $\geq 3 \times$ ULN AND total bilirubin $> 2 \times$ ULN at any point in the study (the elevations do not have to be at the same time or within a specified timeframe), irrespective of ALP, please follow the instruction below:

- Have participant interrupt study drug.
- Notify Incyte study team without delay.
 - The investigator, or designee, should contact the medical monitor to discuss and agree upon an approach for the study participant's follow-up and the continuous review of data.
- Monitor the participant until liver biochemistry parameters and appropriate clinical symptoms and signs return to normal or baseline levels, or as medically indicated.
- Investigate the etiology of the event and perform any relevant diagnostic investigations as discussed with the medical monitor.
- Enter the laboratory data into the laboratory CRF as soon as possible.
- If at any time (in consultation with the medical monitor) the PHL case meets serious criteria, report it as an SAE using standard reporting procedures.

REVIEW AND ASSESSMENT

No later than 3 weeks after the biochemistry abnormality is initially detected and the criteria for PHL is met, the medical monitor, Incyte pharmacovigilance physician, and investigator will discuss and review available data and agree on whether there is an alternative explanation for the elevations in liver biochemistry other than drug-induced liver injury caused by the study drug. Participant matter experts will be included in the review as appropriate.

Evaluation of Alternative Causes

In order to gather additional clinical information to seek other possible causes of the observed liver test abnormalities, the following alternative etiologies should be considered, including but not limited to:

- Active viral hepatitis
- Alcoholic and autoimmune hepatitis

- Hepatobiliary disorders
 - Biliary tract disease, such as migration of gallstones or intrahepatic lesions, more often causes cholestatic injury initially and should be investigated with gall bladder and ductal imaging studies, especially if alkaline phosphatase is increased. Malignant interruption of the biliary tract also should be considered.
- Concomitant treatment
- Other causes such as systemic infections (eg, bacterial, fungal, viral), nonalcoholic steatohepatitis, and cardiovascular diseases

Actions After Review and Assessment

According to outcome of the review and assessment, please follow the instructions below:

If there **is** an agreed alternative explanation for the AST or ALT **and** total bilirubin elevations, a determination of whether the alternative explanation is an AE will be made and subsequently whether the AE meets the criteria for an SAE.

- If the alternative explanation is not an AE, record the alternative explanation on the appropriate CRF if possible.
- If the alternative explanation is an AE/SAE, record the AE/SAE in the eCRF accordingly and follow the standard study processes.
- Have participant resume study drug as per Protocol guidelines.

If it is agreed that there is no explanation that would explain the AST or ALT and total bilirubin elevations:

- Have participant permanently discontinue study drug and perform end-of-treatment procedures.
- Report an SAE (report term "Hy's Law").
 - The 'medically important' serious criterion should be used if no other serious criteria apply.
 - As there is no alternative explanation for the Hy's law case, a causality assessment of related should be assigned.
- If there is an unavoidable delay of over 3 weeks in obtaining the information necessary to assess whether or not the case meets the criteria for a Hy's law case, then it is assumed that there is no alternative explanation until such time as an informed decision can be made. Report an SAE (report term "Potential Hy's Law") applying serious criteria and causality assessment as per above.

ACTIONS REQUIRED FOR REPEAT EPISODES OF AST OR ALT > 3 × ULN AND/OR TOTAL BILIRUBIN > 2 × ULN

The requirement to conduct follow-up, review, and assessment of a repeat occurrence(s) of PHL is based on the nature of the alternative cause identified for the previous occurrence.

If the alternative cause for the previous occurrence of PHL was not chronic or progressing malignant disease, please follow the process for PHL review and assessment as described in this appendix.

If the alternative cause for the previous occurrence of PHL was chronic or progressing malignant disease, please follow the instructions below:

- Determine whether there has been a significant change* in the participant's condition.
 - If there is no significant change, no action is required.
 - If there is a significant change, follow the process described for PHL review and assessment as described in this appendix.

* A 'significant' change in the participant's condition refers to a clinically relevant change in ALT, AST, or total bilirubin, or associated symptoms. The determination of whether there has been a significant change will be at the discretion of the investigator; this may be in consultation with the medical monitor if there is any uncertainty.

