6.6.3. Criteria and Procedures for Dose Interruptions and Modifications of Study Drug

Safety concerns should be discussed with the sponsor immediately upon occurrence or awareness to determine if the participant should continue or discontinue study treatment.

Guidelines for interruption and restarting of itacitinib IR are provided in [Table 14](#).

6.6.3.1. Part 1

In Part 1, dose interruptions are permitted for individual study participants; dose modifications will not be permitted during the DLT evaluation period. The occurrence of DLTs and other toxicities (related or unrelated to study drug) will guide decisions for treatment interruptions and discontinuation for individual participants. In order to be considered evaluable in Part 1, participants must receive at least 42 of the 56 doses of study drug at the assigned dose level during the 28-day DLT evaluation period or have experienced a DLT during the first 28 days.

6.6.3.2. Part 2

Table 14: Guidelines for Interruption and Restarting of Study Drug

| Adverse Event | Action Taken |
|---|--|
| Chemistry | |
| Grade 4 increase in ALT and/or AST | 
Step 1: Interrupt study drug. Assess ALT or AST every 7 days until the toxicity has resolved to \leq Grade 1.
 
Step 2: If assessed as not related to study drug, restart study drug at same dose. If assessed as related to study drug, restart study drug at a dose 100 mg BID less than the previous dose.
 
Note: If liver tests indicate a potential Hy's Law case ($ALT > 3.0 \times ULN$, $ALP < 2 \times ULN$, and $\text{bilirubin} \geq 2.0 \times ULN$), interrupt study treatment, conduct a full work-up (including imaging if clinically indicated) to evaluate other immediately apparent possible causes of aminotransferase elevation and hyperbilirubinemia, including but not limited to, viral hepatitis, pre-existing chronic or acute liver disease, or the administration of other drug(s) known to be hepatotoxic. If Hy's Law can't be unequivocally ruled out, permanently discontinue study treatment.
 |
| Hematology | |
| Grade 4 thrombocytopenia or Grade ≥ 3 thrombocytopenia with bleeding | Interrupt dose and assess platelet count every 7 days until toxicity resolves to \leq Grade 1 or to baseline platelet count; restart study drug at 100 mg BID less than the previous dose. |
| Grade 4 thrombocytopenia and clinically significant bleeding event | Permanently discontinue study drug. |

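### Table 14's potential Hy's Law note conflicts with Appendix E on enzyme, ALP and stop standard and does not refer to it: a minor safety correction affecting at most 4 participants

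*Combined protocol and SAP*

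**What the plan says.** **Table 14, Section 6.6.3.** The row for a Grade 4 rise in ALT and/or AST interrupts the drug and then directs: "Assess ALT or AST every 7 days until the toxicity has resolved to" Grade 1 or lower. For the restart it says: "If assessed as related to study drug, restart study drug at a dose 100 mg BID less than the previous dose". If the event is unrelated: "If assessed as not related to study drug, restart study drug at same dose". The row for other Grade 3 toxicities has the same two steps. A note in the ALT/AST row defines a potential Hy's Law case by ALT > 3.0 x ULN, ALP < 2 x ULN and bilirubin ≥ 2.0 x ULN. It calls for interruption and a work-up, and ends: "If Hy's Law can't be unequivocally ruled out, permanently discontinue study treatment". The note does not name AST as a trigger, is silent on timing and does not mention Appendix E.

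**Appendix E.** A potential case is AST or ALT > 3 x ULN with total bilirubin > 2 x ULN at any time on study. The branch for criteria met uses AST or ALT ≥ 3 x ULN and specifies "the elevations do not have to be at the same time or within a specified timeframe), irrespective of ALP". That branch interrupts the drug and requires a three-party review within 3 weeks. If the parties agree that nothing else explains the elevations, the drug stops permanently and an SAE is reported. If they agree on another explanation, the drug may resume under the protocol's guidelines. Only participants who do not meet the criteria are sent to Section 6.6.3.

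**Elsewhere.** Section 9.3 refers the reader to Appendix E for managing these cases. Table 11 excludes ALP ≥ 2.5 x ULN at screening. Section 4.1 records 4 treated participants and closed enrollment; those still on drug continue in the extension period.

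**The concern.** One term carries two sets of criteria, in the two places a site would look when liver tests rise. Table 14 is the place to look up interruption and restart, and its note reads as complete. A site that used only that table could decide that an AST-only or high-ALP case is not a potential Hy's Law case and apply the ordinary Grade 4 or other-Grade-3 row. In those rows, judging the event drug-related leads to a lower dose. In Appendix E, elevations with no explanation other than the drug lead to permanent discontinuation. At stake is a drug-stopping rule for people who remain on itacitinib IR, not any estimate or test.

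**Working it through.** The plan gives no figure to reproduce, so this is a comparison of rules.

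**1. The triggers, in multiples of ULN**
- Table 14 note: ALT > 3.0 and ALP < 2 and bilirubin ≥ 2.0.
- Appendix E definition: (AST or ALT) > 3 and total bilirubin > 2.
- Appendix E branch for criteria met: (AST or ALT) ≥ 3 and total bilirubin > 2, any ALP, any timing.

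**2. Test profiles**

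| Profile | Table 14 note | Appendix E definition | Appendix E criteria met |
|---|---|---|---|
| ALT 4, AST 1, ALP 1, bilirubin 2.5 | yes | yes | yes |
| ALT 1, AST 4, ALP 1, bilirubin 2.5 | no | yes | yes |
| ALT 4, AST 4, ALP 2.2, bilirubin 2.5 | no | yes | yes |
| ALT 4, AST 4, ALP 1, bilirubin 2.0 | yes | no | no |
| ALT 3.0, AST 1, ALP 1, bilirubin 2.5 | no | no | yes |

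A grid of 5 ALT x 5 AST x 6 ALP x 4 bilirubin values has 600 points. Comparing the note with the criteria-met branch, 40 points meet both, 212 meet Appendix E only, 20 meet the note only and 328 meet neither. All 20 note-only points have bilirubin exactly 2.0. These are checks of logic; the counts depend on the grid chosen and are not event rates.

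**3. The entry limit for ALP.** Table 11 admits ALP < 2.5 x ULN and the note requires ALP < 2 x ULN. For ALP from 2.0 to < 2.5 x ULN, a participant is eligible but cannot meet the note while ALP stays there. This follows from the two limits alone.

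**4. Consequence for a Grade 4, AST-only, drug-related event with bilirubin > 2 x ULN, at 300 mg BID**
- Table 14 row alone: interrupt, check weekly to Grade 1 or lower, restart at 300 − 100 = 200 mg BID.
- Appendix E: interrupt, review within 3 weeks, and discontinue permanently if no other explanation is found.

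The other-Grade-3 row gives the same contrast. The documents do not give CTCAE cut-offs, so nothing here relies on the row for Grade 1 or 2 events.

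**5. Stop standards.** Table 14 stops the drug unless Hy's Law is unequivocally excluded. Appendix E allows it to resume on an agreed alternative explanation. Appendix E also presumes no alternative explanation when the information takes more than 3 weeks, which leans the same way as Table 14. The two therefore part only where a cause is agreed but not certain.

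**6. Internal variation.** In the text as read from the PDF, Appendix E has > 3 in its definition and ≥ 3 in its action branch, and bilirubin ≥ 2 in one heading and > 2 in the text. This matters only at exact boundary values, and the signs need checking in the source.

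**The case against.** The strongest reply is that the plan already covers these cases. Section 9.3 sends their management to Appendix E. Appendix E screens every AST or ALT > 3 x ULN or bilirubin > 2 x ULN result, interrupts the drug when its criteria are met, and passes on only the remainder to Section 6.6.3. That stands. A reader might infer that AST-only and high-ALP cases go uncaught, or that a participant entering with ALP of 2.0 to < 2.5 x ULN has no Hy's Law protection. Neither is supported: in that band only the note's wording fails, Appendix E still applies, and nothing shows that any of the 4 participants entered there.

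A premature restart would also have to get past other safeguards. Section 6.6.3 says: "Safety concerns should be discussed with the sponsor immediately upon occurrence or awareness". Section 6.6 asks for consultation with the medical monitor whenever possible, and Section 6.6.4 limits treatment delays for a persistent AE to 3 weeks unless the sponsor approves longer. In the Grade 3 and Grade 4 rows used above, the drug is interrupted in any event. These points lower the likelihood of error but do not reconcile the criteria.

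Nor is the note simply the weaker rule. It is wider at bilirubin exactly 2.0 x ULN, and its stop wording is stricter.

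Finally, Table 14 is printed under the Part 2 heading, and Part 2 no longer applies. Read literally, Appendix E would be the only rule in force. But Section 6.6.3 introduces the table without limiting it to Part 2 ("Guidelines for interruption and restarting of itacitinib IR are provided in" Table 14), and Appendix E refers back to that section. Reading it as live for ongoing participants is reasonable, but it is an interpretation that the text should settle.

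**Conclusion.** The two criteria conflict as written. The note omits AST-only cases and cases with ALP ≥ 2 x ULN, the stop standards differ, and Table 14 does not refer to Appendix E. It would be too strong to say that nothing gives Appendix E priority: Section 9.3 and the appendix's own workflow imply it. What is missing is an explicit precedence statement and a pointer from the dosing table.

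This is a minor safety correction. At most 4 participants are exposed, the number still on drug is not stated, and no analysis, sample size or error rate changes. Harm would require a site to use Table 14 without Appendix E and then to restart despite sponsor and medical monitor contact. The conclusion assumes that Table 14 applies to ongoing Part 1 participants. The conflict over AST and ALP does not depend on the > and ≥ signs.

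**What to change.** 1. Replace the criteria in the Table 14 note with a statement that any AST or ALT ≥ 3 x ULN, or total bilirubin ≥ 2 x ULN, is assessed first under Appendix E. If its criteria are met, Appendix E governs interruption, restart and discontinuation for that liver event, in place of the ALT/AST and other-toxicity rows. State that this applies to ongoing Part 1 participants.
2. After checking the signs against the source PDF, use one set of cut-offs in both places: AST or ALT ≥ 3 x ULN and total bilirubin ≥ 2 x ULN, irrespective of ALP and timing. All five profiles above then qualify. No current case is lost, since this rule contains all three existing ones, and cases are added only at bilirubin exactly 2.0 x ULN.
3. Keep the stricter stop standard in both places: discontinue permanently unless the Appendix E review rules out Hy's Law by an agreed alternative explanation. Keep Table 14's restart level of Grade 1 or lower.

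The cost is wording, by amendment or clarification letter. No new test is needed: AST, ALT, ALP and total bilirubin are in the Table 15 chemistry panel, which Table 4 already schedules at extension visits. The downside is possibly a few extra temporary interruptions among at most 4 people.

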APPENDIX F. COVID-19 PANDEMIC MITIGATION STRATEGIES AND INSTRUCTIONS

The COVID-19 global pandemic presents challenges to the ongoing conduct of clinical trials. In line with regulatory guidance regarding clinical trial execution during the pandemic, the sponsor has issued the following Protocol considerations to ensure participant safety is maintained and adequate benefit/risk analyses are applied relative to participation in the study and the completion of study procedures and objectives while maintaining the investigational product supply chain.

Recognizing the dynamic nature and flexibility required to manage the impact of the pandemic on this clinical trial, additional details will be incorporated into respective study manuals and site-specific monitoring plans as applicable, with institutional requirements as warranted, and communicated and discussed with investigative sites as needed. Relevant test results will be documented in the eCRF, and applicable changes to the ICF will be made and monitored.

SARS-CoV-2 Infection and Participation in the Study

During the COVID-19 pandemic, additional risks to participants exist either related to going to a healthcare facility or as a result of study-related activities. It is at the principal investigator's discretion to balance the risk/benefit while considering the participant's safety. In addition, country-specific requirements are to be followed with regard to COVID-19 testing.

A participant who fails screening due to SARS-CoV-2 infection may repeat the screening process upon recovery and COVID test normalization.

Study Site Visits

If local travel restrictions, isolation requirements, or the investigator's benefit/risk assessment determines it to be unsafe for participants to attend study visits at the investigational site, the site staff may elect to pursue the following:

- In order to minimize participant risk, study visits may be conducted via telemedicine modalities (phone or video) or as per site institutional guidelines. At a minimum, a review of AEs and concomitant medications must be completed. On-site visits should be conducted whenever feasible and are required for administration of study treatment. The participant may also be asked to undergo additional safety laboratory assessments.
- In order to support investigator oversight of participant safety and disease management, the participant may be asked to undergo some laboratory tests or study procedures (eg, imaging) at a local laboratory or facility closer to the participant's residence rather than at the investigational site. In this case, the study physician will provide the participant with the list of parameters to be checked. These tests should be performed in certified laboratories and the investigator must ensure data can be transferred to the investigational site.

- Some tests, such as MRI assessments, may require longer windows due to the COVID-19 pandemic and may be performed outside the regularly scheduled visit window or may be conducted at the next scheduled visit. It is the investigator's responsibility to check with the facility (if performed at a different facility) that the data will be obtained and available for evaluation. General procedures performed outside of Protocol time windows will be captured as Protocol deviations due to COVID-19 in the eCRF.

Study Treatment Management in the Event of SARS-CoV-2 Infection

If a participant develops a SARS-CoV-2 infection, the event should be reported as an SAE (if it meets the SAE definition requirements) and appropriate medical intervention provided.

Postbaseline COVID-19 testing should follow country-specific requirements depending on the extent of COVID-19 pandemic, local institutional guidance, or the investigator's clinical judgment.

For participants who are diagnosed with COVID-19 during the study (positive COVID-19 test) or presumed (test pending/clinical suspicion) affected by SARS-CoV-2 infection, study treatment should be delayed until COVID-19 test normalization and clinical recovery. Prior to restarting treatment, the study medical monitor should be notified with the participant's condition, that is, the participant should be afebrile for 72 hours and SARS-CoV-2-related symptoms (if any) should have recovered for a minimum of 72 hours.

Safety monitoring following COVID-19 infection should be implemented as per institutional guidance or clinical judgment (eg, coagulation factors). Concomitant medication administered for treatment of SARS-CoV-2 infection should be carefully considered for potential drug-drug interactions and recorded in the clinical database (EDC).

COVID-19 Vaccination

Participants may receive the COVID-19 vaccine as long as it is not a live vaccine. COVID-19 vaccination will be captured in the eCRF as a concomitant medication. Administration of study treatment may be delayed to ensure vaccination is completed and acute AEs (if any) are managed. The medical monitor may be consulted if needed.

Clinical Trial Monitoring

Study monitoring visits could be postponed; however, the site monitor and sponsor will continue to employ off-site monitoring practices such as routine communication methods (eg, phone calls, emails, video visits) with the sites to get information on trial progress, participant status, and information on issue resolution. The study monitor may remotely review data entered into the EDC for accuracy and completeness if allowed by the national regulatory body, investigational site, and/or in compliance with local authorities.

Reimbursement of Additional Expenses

The sponsor will reimburse for any extraordinary expenses, keeping appropriate documentation as evidence (eg, travel expenses for the local laboratory visit[s], the costs of local [proximate] laboratory tests).

